4 RESEARCH QUESTION/AIM(S)

The purpose of the present study is to test whether theory and evidence-based alternative communication formats, targeting message specificity and previously identified psychosocial predictors of adherence, could improve the behavioural impact of existing alert systems, compared to the official messages sent in association with the UK AQIs.

Research questions

Primary questions:

1) What is the main effect of using behaviourally enhanced messages, compared to the currently used DAQI messages, to present the health advice associated with air quality notifications for a hypothetical high air pollution scenario on adherence intentions?

Prediction:

A) The behaviourally enhanced messages will lead to stronger intentions to adhere to recommendations.

2) What is the main effect of using a behaviourally enhanced message, compared to the currently used DAQI messages, to present the health advice associated with air quality notifications on actual behaviour changes at four weeks?

Prediction:

A) The enhanced messages will lead to greater behaviour changes.

3) In case of a real alert being issued during the study period, how do the different messages affect actual behaviour change?

Prediction:

A) The enhanced messages will lead to greater behaviour change.

Secondary questions:

4) If there is a format effect, which variables mediate the relationship between the information format and behaviour change?

5) Which factors are associated with greater behaviour change across all groups?

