For the purpose of the current study, KCL will launch an alternative version, which will allow the researchers to send different types of messages for the control and intervention groups during the study period. To increase message relevance, targeted advice will be sent to people with lung and/or heart or other existing condition, and the generally healthy public (see Table 3). It is worth noting that the current UK AQI does not provide targeted advice for people with heart conditions apart from reducing exertion, and the main advice for people with lung conditions is to consider using their reliever inhaler more often. Usually CityAir sends alerts for moderate, high and very high air pollution to users in the at-risk group, whilst sending only alerts for high and very high air pollution to users in the other groups. However, for the purpose of the current study, the alternative version of the application also will send moderate alerts and associated advice to the general population group. This will allow to actually test the UK AQI advice in case of a real moderate air pollution episode during the study period. To keep the study design simple, we will not differentiate between cyclists, joggers, and pedestrians. However, general messages also will include advice on how to adjust these types of physical activity to reduce exposure. Personal device IDs (i.e. an anonymous and unique identifier attributed to an individual mobile device) will be used to link

questionnaires completed at different time points by the same study participant. At the end of the study, a new version of CityAir will be issued to allow the application to go back to its usual functions.

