5.4.2 Recruitment and study procedure

All CityAir application users will be sent a notification about the current study containing a link to the participant information sheet. If eligible and happy to take part in the study, then they will be redirected to an online survey, using a well-known online platform (<https://www.surveymonkey.co.uk/>).

Once potential participants had agreed to take part, they will be asked to indicate whether they had a pre-existing health condition. Based on their answers, they will be divided into two groups (general public and at risk respondents). Respondents in both groups will be randomised via an algorithm run by CityAir to either a control or intervention condition.

Participants will be asked to read the scenario of a hypothetical high pollution episode and to indicate their intentions to follow the health advice given (i.e. baseline adherence intentions measure). After completion of the first questionnaire, all participants will be able to receive real-time CityAir notifications about real air pollution episodes. Whilst the control group will receive air quality notification and associated health advice in the usual UK AQI format, the intervention group will receive health advice in an alternative format (see Materials).

5.5 MATERIALS:

Table 2 shows the health advice accompanying air quality alerts in both the usual and alternative format (i.e. targeting message specificity). Table 3 shows some of the additional messages that will be sent to the intervention group and targeting specific psychosocial factors identified in our previous systematic review. Readability scores were calculated for all messages (using a readability tool available at: <https://www.webpagefx.com/tools/read-able/check.php>) and reported in Tables 2-3. To reduce the likelihood of confounding effects, the alternative messages have a similar word count and identical readability scores of 8 (i.e. they should be easily understood by 13 to 14 years old).

SHORT TITLE/ACRONYM: Improving the health impact of air quality alerts v.3

Table 2 The health advice associated with the current UK AQI compared with the alternative/more detailed health messages developed for this study.

Level of pollution	Usual messages of UK AQI*		Alternative messages (targeting message specificity)	
	General public	At risk	General public	At risk

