Moderate 4-6	Enjoy your activities as usual ^a	Adults and children with lung problems, and adults with heart problems, who experience symptoms, should consider reducing strenuous physical activity, particularly outdoors. ^b	
Enjoy your activities as usual. However, if you wanted you, you can reduce your exposure to pollution by reducing levels and length of physical activity outdoors.
 
You can also consider changing:
 
 • Travel route or • Exercise location (e.g. use our app to find less polluted roads or parks) or • Time (e.g. mornings or less polluted times). ^e 	
Adults and children with lung problems, adults with heart problems, and older people, should reduce levels and length of physical activity outdoors.
 
Where possible, change:
 
 • Travel route or • Exercise location (e.g. use our app to find less polluted roads or parks) or • Time (e.g. mornings or less polluted times). ^h
High 7-9	Anyone experiencing discomfort such as sore eyes, cough or sore throat should consider reducing activity, particularly outdoors. ^c	Adults and children with lung problems, and adults with heart problems, should reduce strenuous physical exertion, particularly outdoors, and particularly if they experience symptoms. People with asthma may find they need to use their reliever inhaler more often. Older people should also reduce physical exertion. ^d	
Anyone who experiences sore eyes, cough or sore throat should consider limiting their exposure to air pollutants.
 
To do this, you don't need to stay indoors, instead you can reduce levels and length of physical activity outdoors.
 
You can also consider changing:
 
 • Travel route or • Exercise location (e.g. use our app to find less polluted roads or parks) or 	
Adults and children with lung problems, adults with heart problems, and older people, should reduce levels and length of physical activity outdoors.
 
People with asthma may find they need to use their reliever inhaler more often.
 
Where possible, change:
 
 • Travel route or • Exercise location (e.g. use our app to find less polluted roads or parks) or

SHORT TITLE/ACRONYM: Improving the health impact of air quality alerts v.3

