6. STATISTICAL ANALYSES

6.1 Quantitative data

ANCOVAs will be performed for all the intentions measures in relation to the high air pollution hypothetical scenario, adjusting for baseline measures collected about one month earlier (target population and intervention/control group entered as fixed factors). Both main and interaction effects will be tested. ANCOVAs will also be performed for the actual behaviour change at 4 weeks (with the intervention/control group entered as fixed factor). These latter analyses will also be ran in the subgroups of healthy and at-risk participants. Chi square tests will be performed to analyse differences in proportion of self-reported actual behaviour change between groups, in relation to a real moderate air pollution episode. A two-way MANOVA (1000 bootstraps) will test whether there are differences between groups (both main effects and interactions) in perceived susceptibility, worry, severity, perceived response efficacy, perception of time, self-efficacy, trust, clarity, credibility and perceived informed choice measures. Multiple linear regressions will be used to assess the associations between main predictor variables and self-reported behaviour change at 4 weeks. Mediations effects of predictor variables on significant behavioural changes will be tested using PROCESS macro (38).

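### Primary question 3 covers a real alert of any level, but the only planned between-arm test is for a moderate episode

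*Combined protocol and SAP*

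**What the plan says.** Section 4 lists question 3 among the primary questions: "In case of a real alert being issued during the study period, how do the different messages affect actual behaviour change". No level is named, and the prediction is that the enhanced messages produce greater change.

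On the levels sent, section 5.4.1 states: "Usually CityAir sends alerts for moderate, high and very high air pollution to users in the at-risk group". Other users ordinarily get high and very high alerts only. For the study, "the alternative version of the application also will send moderate alerts and associated advice to the general population group", and the reason given is: "This will allow to actually test the UK AQI advice in case of a real moderate air pollution episode during the study period". Table 2 (section 5.5) gives usual and alternative wording at all three levels for both populations.

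Section 6.1 has one quantitative analysis of behaviour after a real alert: chi-square tests of "differences in proportion of self-reported actual behaviour change between groups, in relation to a real moderate air pollution episode". It does not say whether 'groups' means the two arms or the four arm-by-population cells. Section 5.4.2 first divides respondents by health status and then states: "Respondents in both groups will be randomised via an algorithm run by CityAir to either a control or intervention condition".

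**The concern.** The question and its analysis differ in scope. The trial delivers arm-specific messages at three levels and asks a primary question about any of them, but plans a test at one. If the study month brought only a high or very high alert, question 3 would have no prespecified comparison, and any analysis would be chosen after the data were seen. If several levels occurred, nothing says which alert counts or how levels are combined.

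A lesser matter is that the test names no target-population term, although the design has two factors and the usual moderate advice differs by population. General-public controls are told only "Enjoy your activities as usual". At-risk controls are addressed as people "who experience symptoms, should consider reducing strenuous physical activity, particularly outdoors". A pooled two-by-two table averages two different message contrasts, and a four-cell test would not isolate the message effect.

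**Working it through.** The main point is textual and rests on no figure. The plan gives no power or precision figure specific to the real-alert test, so there is none to reproduce.

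**Scope, side by side**
- Question 3: a real alert, no level stated.
- App (5.4.1): moderate is added for the general population; no level is removed.
- Table 2: 3 levels × 2 populations × 2 formats = 12 message cells, 4 at each level. The planned test covers the 4 moderate cells; 12 − 4 = 8 have no between-arm test of alert behaviour.
- Other analyses in section 6: the intentions ANCOVAs use a hypothetical high scenario. The 4-week item asks how often action was taken over four weeks after an air quality forecast, so it can reflect high alerts only in part. The content analysis in 6.2 does not compare arms.

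**What stratifying by population would do**

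Inputs:
- Target of 240 with a 20% dropout allowance (5.3). Taken as 240 × 0.8 = 192 completers, 96 per arm.
- A 36% behaviour rate, the review median in 1.1.5, and 9.7%, the bottom of that range. Applying these rates here is an assumption.
- A 60:40 split of general public to at-risk, also assumed.

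The 95% half-width for an arm difference, in points, is 196 × √(2p(1 − p)/n), with the same rate p in both arms and n per arm.

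| Case | n per arm | Half-width |
|---|---|---|
| Pooled, p = 0.36 | 96 | 196 × √(0.4608/96) = 13.6 |
| General public | 57.6 | 17.5 |
| At-risk | 38.4 | 21.5 |
| Pooled, half respond | 48 | 19.2 |
| General public, half respond | 28.8 | 24.8 |
| At-risk, half respond | 19.2 | 30.4 |

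Stratified against unstratified:
- Equal rates of 36%: 13.6 either way.
- Rates of 9.7% (general public) and 36% (at-risk): the mean rate is 0.6 × 0.097 + 0.4 × 0.36 = 0.2022. Unstratified: 196 × √(2 × 0.2022 × 0.7978/96) = 11.4.
- The within-stratum variance is 0.6 × 0.097 × 0.903 + 0.4 × 0.36 × 0.64 = 0.1447. Stratified: 196 × √(2 × 0.1447/96) = 10.8.

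Sensitivity: with 240/1.2 = 200 completers the three full-response half-widths are 13.3, 17.2 and 21.0. Over rates from 9.7% to 70.7% (widest at 50%) they run 8.4–14.1 pooled, 10.8–18.3 for the general public and 13.2–22.4 for at-risk.

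**The case against.** The strongest reply is that testing at moderate level was deliberate. That stands: 5.4.1 says so. But the sentence explains why moderate alerts were added for the general population. It neither excludes other levels nor narrows question 3.

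Other parts of the case against also stand and limit the point:
- A reader might infer from Table 4 that responses to high and very high alerts will certainly be collected, because the behaviour items name no level and the recall options include both. This does not follow. A recall item must offer wrong answers, and the list includes 'Low', for which the app description and Table 2 give no alert or message. The documents do not say which levels trigger a questionnaire.
- A reader might infer that high alerts have no planned analysis at all. Section 6.2 plans content analysis of barriers and facilitators after alerts, with no level limit, and the 4-week item is compared by arm. What is missing is a between-arm test specific to such alerts.
- The absent population term is not a contradiction. Question 3 asks for no effect by population, and the 4-week behaviour ANCOVA also enters arm only, with subgroup runs added. The intentions ANCOVAs and the MANOVA do model both factors, so practice within 6.1 is mixed.
- The gain from stratifying is small. The case that shows one assigns a range minimum and a median to the two populations, and 1.1.5 does not report those rates by population.

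**Conclusion.** The level mismatch holds on the text and should be reconciled, because it leaves part of a primary question without a prespecified between-arm test. Its practical size cannot be given: 8 of 12 message cells is a count of messages, and the frequency of high and very high alerts is not stated.

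It would be tempting to say that leaving out target population biases the test. It does not: a pooled comparison of randomised arms at moderate level is a valid average. Stratifying is a small improvement. It costs no pooled precision (13.6 against 13.6 points) and gains little (11.4 to 10.8), under assumed rates, split and full response. Estimates within one population would be imprecise, about ±17 to 22 points on the same assumptions and about ±25 to 30 if only half respond. They are suited to description only.

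**What to change.** Choose one of two routes.

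1. Delete 'moderate' in 6.1, so that the test covers any real alert level issued.
2. If only moderate alerts are meant, narrow question 3 to say so.

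Under either route, state that 'groups' means the two message arms. Because respondents are divided by target population and then randomised, replace the plain chi-square with a Cochran-Mantel-Haenszel test stratified by target population, as follows:
- run it separately at each alert level for each behaviour item;
- use each participant's first response at that level;
- code the outcome as yes against no or not sure;
- combine high and very high if sparse, still with one response per participant;
- report arm differences by population descriptively, with 95% confidence intervals.

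Also state which alert levels trigger the questionnaire.

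The cost is a sentence or two in the plan and a little more analysis; the behaviour items already exist. The downside of the first route is multiplicity. Table 4 has five behaviour items, so three levels give up to 5 × 3 = 15 tests instead of 5, and results should be read with that in mind. Results at the higher levels may be imprecise, or there may be none. The second route adds no tests but leaves any responses to higher alerts outside the primary question.

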5.6 MEASURES

Table 4. Summary of measures.

Timing	Measure	How it will be measured
First Online Questionnaire – After reading hypothetical high air pollution scenario	Baseline intentions ^a to adopt protective behaviours in response to hypothetical, high air pollution alert	Assuming the situation described was happening right now, how much would you agree with the following statements? 
 - I intend to follow the recommendations received with the air alert to reduce exposure to air pollution - I will avoid going outdoors - I intend to reduce length or level of my physical activity outdoors - I intend to change my travel route - I intend to change my exercise location - I intend to change the time when I travel - I intend to change the time when I exercise outdoors
	Baseline medication adherence intentions ^a	If you have lung problems: 
 - I intend to use my preventer inhaler daily - I intend to carry my reliever inhaler with me
	Other baseline intention ^a (not advised behaviours)	
 - I will wear a mask as a protection from air pollution - I intend to reduce length or level of my physical exercise indoors
	Previous protective behaviour ^b	- In the past 4 weeks, how often have you taken action to reduce exposure to air pollution, I response to hearing or reading an air quality forecast?
	Planning	
 - In the last 4 weeks, to reduce your exposure to air pollution, have you considered making permanent changes to your daily travel route or exercise place and time?^c - In the last 4 weeks, how often have you checked air quality information before doing physical activity outdoors?^b
	Physical activity ^d	- To stay healthy, the NHS recommends at least 150 minutes of moderate physical activity (e.g. cycling, fast walking, swimming) every week (e.g. 30 minutes 5 days a week). Based on this, how physically active were you in the last week?
	Symptoms ^c	- Have you ever experienced symptoms caused by air pollution?
Air Alert period – Online questionnaires	Alert recall ^e	- Recently we sent you an air quality alert about poor air quality. What was the level of air pollution reported?

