	Actual Behaviour change ^c	In response to receiving the air quality alert: 
 - I reduced length or level of my physical activity outdoors - I changed my travel route - I changed my exercise location - I changed the time when I travelled - I changed the time when I exercised outdoors - If you answered no, please report the reasons [text box].
	Medication adherence ^c	If you have lung problems: 
 - I used my preventer inhaler daily - I carried my reliever inhaler with me when going outdoors. - If you answered no, please report the reasons [text box].
Final Online Questionnaire – at 4 weeks	Behaviour change at 4 weeks ^b	- In the past 4 weeks, how often have you taken action to reduce exposure to air pollution, I response to hearing or reading an air quality forecast?
	Physical activity ^d	- To stay healthy, the NHS recommends at least 150 minutes of moderate physical activity (e.g. cycling, fast walking, swimming) every week (e.g. 30 minutes 5 days a week). Based on this, how physically active were you in the last week? ^e
	Action planning	
 - In the last 4 weeks, to reduce your exposure to air pollution, have you considered making permanent changes to your daily travel route or exercise place and time?^c - In the last 4 weeks, how often have you checked air quality information before doing physical activity outdoors?^b
	Worry ^a	Adapted from Witte et al. (34) 
 - The information received through the CityAir app made me worry about the possibility of suffering health effects from exposure to air pollution

	- The information received through the CityAir app made me nervous and tense about the possibility of suffering health effects from exposure to air pollution
Severity ^a	Adapted from Witte et al. (34)
	- Air pollution is a severe threat to my health
Conditional susceptibility ^f	- How likely do you think you are to suffer from health effects due to air pollution if you do not take any action to reduce exposure? - How likely do you think people of your same age and sex are to suffer from health effects due to air pollution if they do not take any action to reduce exposure?
Response efficacy ^a	Adapted from Witte et al. (34)
	- Following the health advice received through the CityAir app is effective in protecting me from exposure to air pollution

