Medication adherence intentions ^a	If you have lung problems: - I intend to use my preventer inhaler daily - I intend to carry my reliever inhaler with me
Other intentions (not advised behaviours) ^a	- I will wear a mask as a protection from air pollution - I intend to reduce length or level of my physical exercise indoors

Notes: ^a Measured on 9-point scales, where 1=strongly disagree to 9=strongly agree; ^b From 1 Not at all to 9 all of the time; ^c Possible answers: yes, no, not sure; ^d From 1 Not at all, to 7 more than 150 minutes; ^e Possible answers: Low, Moderate, High, Very High, Not sure, I did not receive any alert; ^f From 1=not at all likely to 9=extremely likely; ^g on a 5-point scale; ^h 1= not clear at all to 9= extremely clear. Demographic data will be collected for all the participants in the first questionnaire.

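### Question 5 asks about behaviour change, but its outcome is a week-4 frequency level and the regression sentence does not bring in the identical baseline item

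*Combined protocol and SAP*

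**What the plan says.** Question 5 in section 4 is secondary and asks: "Which factors are associated with greater behaviour change across all groups". Section 6.1 answers it with one sentence: "Multiple linear regressions will be used to assess the associations between main predictor variables and self-reported behaviour change at 4 weeks". The predictors are not listed, and neither a baseline value nor study arm is mentioned.

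Table 4 (section 5.6) labels the outcome "Behaviour change at 4 weeks". The item itself begins "In the past 4 weeks, how often have you taken action to reduce exposure to air pollution" and is scored "From 1 Not at all to 9 all of the time". No change score is defined anywhere. The first questionnaire carries the same item on the same scale, as *Previous protective behaviour*.

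Elsewhere in 6.1 the intentions ANCOVAs are described as "adjusting for baseline measures collected about one month earlier". The ANCOVA of the week-4 behaviour item names arm as fixed factor and names no covariate. The mediation sentence (PROCESS) names no covariates either.

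**The concern.** The label says change, but the number analysed is how often someone acted. Someone who acted often before the study and still does scores high without having changed.

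Two features of the design make this matter. Participants are existing users of the alert app, so protective habits can differ between them before randomisation. And Table 4 places worry, severity, susceptibility, response efficacy, self-efficacy and response costs only in the final questionnaire, at the end of the period that the outcome looks back on. No earlier belief measure exists, so the baseline behaviour item is the main collected means of separating habit from change.

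At stake is the answer to question 5: a belief that only marks a long-standing habit could be reported as a factor linked to change. The same confounding can enter the belief-to-behaviour path of a mediation model for this outcome, because beliefs are not randomised.

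**Working it through.** **Analysable n.** Section 5.3 states a minimum of 240 after 20% inflation, and 240 / 1.2 = 200. As a check, ANCOVA power (one numerator degree of freedom, one covariate, alpha 0.05, 80% power) at f = 0.20 needs 199, and 199 x 1.2 = 238.8, in line with 240. The printed f = 0.02 would need 19,625. That is a separate matter; here only n of about 200 is used.

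**Assumptions, not in the documents.** Let ρ be the correlation between the baseline and week-4 items, taken as 0.3 to 0.7, and r the correlation between a belief and the baseline item, taken as 0.1 to 0.5. The belief has no link to week-4 behaviour given baseline.

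**Spurious correlation with the week-4 level.** It equals ρ × r, from 0.3 × 0.1 = 0.03 to 0.7 × 0.5 = 0.35.

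**How often it is declared significant.** Fisher's z at n = 200, two-sided 5%, with z = atanh(ρr) × √197:
- 0.6 × 0.3 = 0.18: z = 0.182 × 14.04 = 2.55, and Φ(2.55 − 1.96) ≈ 0.72.
- 0.3 × 0.1 = 0.03: z = 0.42; both tails together ≈ 0.07.
- 0.7 × 0.5 = 0.35: z = 5.13; above 0.99.

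Simulation with n = 199 and 2,000 data sets per setting, regressing the week-4 level on the belief alone:

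| ρ | r = 0.1 | r = 0.2 | r = 0.3 | r = 0.5 |
|---|---|---|---|---|
| 0.3 | 7% | 14% | 25% | 56% |
| 0.5 | 10% | 29% | 55% | 94% |
| 0.7 | 16% | 51% | 85% | over 99% |

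With the baseline item added, the rate is 4% to 6% in every cell.

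**If the baseline item measures habit with error.** Take reliability 0.7 (assumed) and observed correlations of 0.6 and 0.3. The belief and week-4 item then correlate 0.18 / 0.7 = 0.257. The partial correlation given the observed baseline item is (0.257 − 0.18) / √(0.91 × 0.64) = 0.077 / 0.763 = 0.10. At n = 200 that gives z ≈ 0.10 × √196 ≈ 1.4 and a rejection rate of roughly 30%. Without the baseline item, z = 0.263 × 14.04 = 3.69 and the rate is about 96%. Adjustment removes most of the excess but not all.

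**Raw change score.** With equal variances, the same belief correlates with week 4 minus baseline at −r × √((1 − ρ)/2) = −0.3 × √0.2 = −0.13. The score replaces a positive artefact with a negative one.

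**Leaving out arm.** If arm shifts the belief and the outcome by 0.4 SD each and the two are otherwise unrelated, the rejection rate is 8%. If arm shifts the belief by 0.8 SD and the outcome by 0.4 SD, it is 17%. With arm in the model it is about 5%.

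**The case against.** A reader might infer that the plan excludes the baseline item and arm. It does not say so. The predictors are unlisted, and the baseline item, arm and target population could all be among them. Other text suggests that adjustment was in mind for this outcome: the week-4 item is analysed by ANCOVA, a term that implies a covariate; the sample size allows for one; and asking the item twice in identical words makes most sense if the first answer is used. This stands as far as it goes. None of it reaches the regression sentence, in a paragraph that states baseline adjustment where the intentions are concerned.

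A reader might also infer that the regressions would find only people who already acted often. That is too strong. The level mixes habit and change in proportions that the documents do not give, and the table above runs from slight to dominant. The calculations also use one belief at a time; in a multiple regression, other habit-related predictors could absorb part of the shared variance.

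On arm, the objection largely succeeds. The effect of omission is small in the first scenario and moderate in the second. If the messages change beliefs and beliefs change behaviour, the between-arm part of the association is signal. Question 5 speaks of all groups together, so adjusting for arm is partly a choice of what to estimate.

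Finally, question 5 is secondary and claims association only. The documents do not say that its results will be used to design later messages.

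**Conclusion.** The point holds as a mismatch between question and analysis. Question 5 is about change; the regression as worded is about a level; the item that would bring the two together is already collected and is not brought in. The documents do not support calling this a stated exclusion.

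The direction is clear whenever a belief and week-4 behaviour are both positively related to prior habit: its association with week-4 behaviour is then overstated as evidence about change. The size rests on the assumed correlations, so the 7% to over 99% range should be read with them, and 72% is one point within it. The return to about 5% depends on a baseline item free of measurement error. The arm term is a minor part of the point.

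**What to change.** In section 6.1:
- List the predictors for the question 5 regressions, and include the baseline *Previous protective behaviour* item and target population in every model.
- Enter the same two variables as covariates in the PROCESS mediation models of the week-4 item.
- Include arm in the question 5 regressions. Where arm is the independent variable of a mediation model, it is already there.
- Describe results as association with week-4 behaviour given baseline behaviour, and note that a single baseline item may leave some confounding by habit.
- Do not use a raw change score in place of adjustment.

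The cost is wording and up to three degrees of freedom (baseline item, target population, arm) out of about 200 participants. All three variables are already collected or assigned.
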